2.2.2. Secondary Efficacy Endpoints

- Proportion of subjects achieving remission on minimal steroid therapy (defined as subjects who had an absence of new or nonhealing lesions while on an oral prednisone/prednisolone dose of ≤ 10 mg/day for ≥ 8 weeks) at Week 60 (i.e. proportion of subjects achieving sustained remission).
- Time to remission while on minimal steroid therapy (defined as time from randomization to the time the subject initially tapered his/her oral prednisone/prednisolone dose to ≤ 10 mg/day and maintained ≤ 10 mg/day of oral prednisone/prednisolone with no new or nonhealing lesions for ≥ 8 weeks) by Week 60.

- Time to initial flare/relapse (defined as the time from randomization to the time that ≥ 3 new lesions appear within 1 month and do not heal spontaneously within 1 week, or to the time when there is an extension of lesions that were present at the randomization visit) by Week 60. For analysis purposes, “1 month” is assumed to be 30 days and “1 week” is assumed to be 7 days.
- Proportion of subjects who did not flare/relapse (defined as subjects who achieved remission on minimal steroid therapy and did not subsequently have a flare of disease) by Week 60.
- Cumulative dose of corticosteroids.

2.2.4. Safety Endpoints

- All AEs
- Frequency of serious adverse events (SAEs).
- Change from Baseline in vital signs.
- Change from Baseline in laboratory (hematology, chemistry, and urinalysis) parameters.
- Immunogenicity as measured by the incidence, titer, and type of human anti-human antibody (HAHA) immune response.

2.2.5. Pharmacokinetic Endpoints

- Plasma (trough) concentrations of ofatumumab.

2.2.6. Pharmacodynamic Endpoints

- Change from Baseline in B-lymphocyte counts in peripheral blood.
- Time to repletion of CD19+ B-cells to either \geq the baseline level or \geq the lower limit of the normal (LLN) range, whichever is lower.
- B-cell depletion and repletion as measured by CD19+ peripheral blood B-lymphocyte count via routine fluorescent activated cell sorting analysis

2.3. Statistical Hypotheses

- The overall null hypothesis is that there is no difference in time to SR on minimal steroid therapy by Week 60, and there is no difference in duration of remission on minimal steroid therapy between subjects in the ofatumumab SC group versus subjects in the placebo group.
- The alternative hypothesis is that ofatumumab SC is superior to placebo in at least one of the co-primary endpoints.

3. STUDY DESIGN

This is a global, multicenter, randomized, double-blind, placebo-controlled, parallel-group study to assess the efficacy, safety, and tolerability of ofatumumab SC in subjects with PV, who have failed a previous attempt to taper steroid dosing (ie, had a disease flare during the taper attempt). The study includes a Core Study Period consisting of a Screening Period (lasting up to 12 weeks), a 56-week Treatment Period, a 4-week Follow-up visit (Week 60). The Core Study Period is followed by an Individualized Follow-up Period which may last for up to 2 years (depending on time to B cell/IgG repletion). In the Core Study Period, subjects will visit the clinic during Screening; at Baseline (Week 0); at Weeks 2, 4, 6, and 8; and then every 4 weeks from Week 8 through Week 60. Subjects will also have structured phone visits between each of the clinic visits from Week 10 through Week 22. After Week 60, subjects who do not transition into the Extension Study (OPV117059) and have not achieved B Cell/IgG repletion, will return to the clinic every 12 weeks for individualized follow-up. It is anticipated that total duration of participation in this study will be approximately 72 weeks (1.4 years) for subjects who exit the study at Week 60, and up to 184 weeks (3.5 years) for subjects who enter the Individualized Follow-up Period.

A Screening Period of 2 to 12 weeks will occur prior to randomization to allow subjects to achieve disease control (no new lesions for ≥ 2 weeks) [Murrell 2008] using a stable oral dose of prednisone/prednisolone (20 mg/day up to 120 mg/day or 1.5 mg/kg/day [whichever is higher] for ≥ 2 weeks). Multiple visits to the clinic are permitted during this Screening Period to assess disease status and to adjust the oral prednisone/prednisolone dose. Once disease control is achieved, subjects who continue to satisfy the eligibility criteria may be randomized. All screening procedures should be completed within 12 weeks of informed consent being given.

At the Baseline Visit (Day 0), approximately 136 eligible subjects will be centrally randomized 1:1 across 2 strata (disease duration [≤ 1 year, > 1 year] and baseline

prednisone dose [<60 mg/day, ≥ 60 mg/day]) to receive SC administration of ofatumumab 20 mg or placebo once every 4 weeks (with an additional 20 mg 'loading' dose at both Week 0 and Week 4) for a total of 56 weeks (total of 17 injections across 15 monthly dosing visits). Two weeks after the first dose of ofatumumab SC or placebo (ie, Week 2), the oral steroid dose will be gradually reduced according to a fixed dose-taper schedule with a goal of reducing (ie, to ≤ 10 mg/day) or eliminating the dose of prednisone/prednisolone.

After the last dose of ofatumumab SC or placebo at Week 56, subjects will be followed-up for a minimum of 4 weeks, with a visit scheduled at Week 60. Subjects completing the study and meeting all entry criteria will be offered the option to participate in an extension study (OPV117059), which will start after completion of the Week 60 visit. If B-cell counts have not recovered by the Week 60 visit, subjects not entering the extension study will remain in an Individualized Follow-up Period until either the CD19+ B-cell counts or circulating IgG levels are \geq LLN or baseline levels (if $<$ LLN) or until 2 years after the last dose of investigational product (whichever comes first). Individualized Follow-up visits will be scheduled every 12 weeks. Subjects who withdraw from treatment will also enter the Individualized Follow-up Period, unless the subject also withdraws consent.

An independent data monitoring committee (IDMC) will evaluate risks relative to benefits through review of safety and efficacy data on an ongoing basis during the study. Any case of suspected or confirmed PML will go through independent PML adjudication and an opinion will be provided to the sponsor.

3.1. Randomization, Stratification and Blinding

Subjects who meet all eligibility criteria will be randomized 1:1 to receive either ofatumumab SC at a dose of 20 mg or placebo; all doses of investigational product will be administered at the study site once every 4 weeks under the observation of the investigator, with the first dose (Week 0) signifying the start of the 56-week Treatment Period.

A central randomization procedure will be used to allocate subjects to the two treatment arms. Because the possibility exists for a small number of subjects in many sites, the randomization will not be stratified by site. Rather, stratification will be made on disease duration (≤ 1 year, > 1 year), and baseline prednisone dose (< 60 mg, ≥ 60 mg). Randomization will be set up to minimize treatment imbalances within stratification factors.

This is a double-blind study. Each site that prepares study injections using the dilution method must designate an unblinded pharmacist (or appropriately-qualified designee) for drug preparation. All other study staff (which includes the investigator, subinvestigators, other site trial staff, the subject, and Sponsor) will be blinded to the treatment allocated to individual subjects.

The blinded study treatment assignments for individual subject will be maintained by a central interactive voice response (IVR) system. Emergency unblinding will be available via the central IVR system.

The investigator or treating physician may unblind a subject's treatment assignment only in the case of an emergency or in the event of a serious medical condition, when knowledge of the study treatment is essential for the appropriate clinical management or welfare of the subject, as judged by the investigator.

If the treatment blind is broken by the site for a subject in the Treatment Period, the subject in question will be withdrawn from the Treatment Period and moved into the Follow-up Period.

The blinded study treatment assignments for individual subjects will be unblinded to the blinded study teams at [REDACTED] Novartis once the database has been frozen once all subjects have completed the Week 60 Follow-up Visit or have discontinued from the treatment period. Investigators and study subjects will remain blinded to the study treatment assignments until conclusion of the Individualized Follow-up Period.

Randomization and unblinding information will be presented in a data listing.

3.2. Screening Period

A Screening Period of up to 12 weeks will allow subjects to achieve disease control (i.e., no new lesions for ≥ 2 weeks) using a stable dose of 20 mg/day up to 120 mg/day (or 1.5 mg/kg/day, whichever is higher) of oral prednisone/prednisolone for ≥ 2 weeks. Once disease control has been attained, subjects may be randomized to treatment, provided they continue to fully satisfy the eligibility criteria.

3.3. Treatment Period

During the 56-week Treatment Period, site personnel will administer all doses of investigational product in the clinic. Subjects must be treated with acetaminophen/paracetamol and an antihistamine (cetirizine or equivalent) 1 to 2 hours prior to each administration of investigational product.

Subjects will remain on the stable daily oral steroid dose achieved during the Screening Period until Week 2, when they will begin tapering their steroid dose with the goal of reducing or eliminating the daily use of steroids. Subjects' daily oral steroid dose will be reduced by 1 dose level every 2 weeks (as discussed in Section 10.6) until the onset of disease flare/relapse. For a subject who experiences disease flare/relapse, the prednisone/prednisolone dose will be increased by 1 to 4 levels per week until disease control is achieved (ie, no new lesions for ≥ 2 weeks [Murrell 2008]). The prednisone/prednisolone taper will then be reinitiated after a 2-week period of disease control. Once the dose is reduced to 10 mg, an attempt at reducing the steroid taper further is made until the first flare/relapse occurs. After the first flare/relapse at or below 10 mg prednisone/prednisolone, further steroid tapering attempts will be made at the investigator's discretion based on the subject's clinical status.

3.4. Follow-up Period and Individualized Follow-up Period

Subjects are followed-up for a minimum of 4 weeks after the last dose of investigational product at the Week 56 visit. The follow-up visit will include B-cell counts and other safety, efficacy, and quality of life assessments.

If B-cell counts have not recovered by the Week 60 visit, subjects not entering the extension study will remain in Individualized Follow-up until either the CD19+ B-cell counts or circulating IgG levels are \geq LLN or baseline levels (if $<$ LLN) or until 2 years after the last dose of investigational product (whichever comes first). The Individualized Follow-up assessments should be scheduled approximately every 12 weeks. Subjects who withdraw from treatment will also enter the Individualized Follow-up Period.

For subjects who participate in the extension study, Week 60 study assessments will be completed before the first dose of ofatumumab SC in the extension study. Assessments from Wk 60 may be utilized to confirm subject eligibility for entry into the extension study.

Subjects who are HBsAg negative, anti-HBc positive, and HBV DNA negative (or if in Japan and HBsAg negative, anti-HBc (HBcAb) negative, but HBsAb positive) must continue HBV DNA polymerase chain reaction (PCR) monitoring at a minimum of every 12 weeks for 6 months after the last dose of study treatment.

3.5. Pharmacokinetic and Pharmacokinetic Substudy

The protocol planned to have a substudy to determine the pharmacokinetics and pharmacodynamics of ofatumumab SC in subjects with PV. The substudy was planned to be conducted at selected study centers and planned to enroll approximately 25 subjects. Subject participation in the substudy was optional and required subject informed consent. A subject was enrolled in the primary study irrespective of whether or not he/she choose to participate in the substudy.

4. PLANNED ANALYSES

4.1. Interim Analyses

There will be no interim analysis as planned in the protocol due to study early termination. This SAP serves only for the final analysis.

4.2. Final Analysis

The study was terminated early and the final analysis will be conducted on the available data.

5. SAMPLE SIZE CONSIDERATIONS

Due to early termination of the study, the sections on sample size assessment in the protocol (sample size assumptions, sample sensitivity, and blinded sample size re-

estimation) are not applicable. They will not be considered in the SAP for final analysis. A total of 69 patients were randomized to this study.

6. ANALYSIS POPULATIONS

6.1. Screening Failure Population

The number of subjects screened and the number of subjects who failed screening will be summarized.

The Screening Failure population will include all screened subjects who fail all the screen procedures or criteria. This will be the population used for the listing of screening failure reasons.

6.2. Intent-to-Treat (ITT) Population

The ITT population will include all randomized subjects regardless of whether or not they received a dose of investigational product (IP). This will be the primary population used for the efficacy analyses.

In the event of a discrepancy between the treatment assigned at randomization and the actual treatment received, subjects will be analyzed according to the treatment to which they were randomized.

6.3. Per Protocol (PP) Population

The PP population will consist of those members of the ITT population who have no major protocol deviations. Throughout the study, protocol deviations will be identified, tracked and reviewed by the clinical management team. Prior to unblinding, a list of rules will be developed to specify what classes of deviations will be considered to be major deviations, and thus, result in exclusion from the PP population.

If the PP population comprises more than 95% or less than 50% of the ITT population, it will not be analyzed. This population will be used for a confirmatory analysis of the co-primary efficacy endpoints and any key secondary efficacy endpoints described in Section [11](#).

In the event of a discrepancy between the treatment assigned at randomization and the actual treatment received, subjects will be analyzed according to the treatment they actually received for the majority of the 56-week Treatment Period.

6.4. Safety Population

The primary population for safety analyses will be the safety population, which will consist of all subjects who were randomized and were administered at least 1 dose of IP.

In the event of a discrepancy between the treatment assigned at randomization and the actual treatment received, subjects will be analyzed according to the treatment they actually received for the majority of the 56-week Treatment Period.

6.5. Pharmacokinetic Population

The PK population will include all subjects in the ITT population providing at least one analyzed PK sample.

In the event of a discrepancy between the treatment assigned at randomization and the actual treatment received, subjects will be analyzed according to the treatment which they actually received.

6.6. Pharmacogenetic Population

The Pharmacogenetic (PGx) population will include all subjects in the ITT population who consented to providing a genetics sample, provided a sample, and did not withdraw their consent.

In the event of a discrepancy between the treatment assigned at randomization and the actual treatment received, subjects will be analyzed according to the treatment they actually received for the majority of the 56-week Treatment Period.

7. TREATMENT COMPARISONS

7.1. Primary Comparisons of Interest

The primary comparisons of interest for this study are:

- ofatumumab SC versus placebo on time to SR on minimal steroid therapy and
- ofatumumab SC versus placebo on duration of remission on minimal steroid therapy.

7.2. Data Display Treatment and Other Sub-group Descriptors

Study treatments will be presented in all tables, listings and figures (TLFs) in the following order: Ofatumumab SC, Placebo.

All tables and figures presenting primary and secondary analysis results will include subgroup results for the stratification factors baseline prednisone/prednisolone dose [<60 mg, ≥ 60 mg] and disease duration [≤ 1 year, >1 year].

8. GENERAL CONSIDERATIONS FOR DATA ANALYSES

All analyses will be conducted using SAS Version 9.2 or higher.

8.1. Multicentre Studies

Since too few subjects were randomized per sites, no region will be defined and region will not be used as stratification factor in any analysis.

8.2. Other Strata and Covariates

The study randomization is stratified by disease duration [≤ 1 year, > 1 year] and baseline prednisone dose [< 60 mg, ≥ 60 mg].

The randomization strata of disease duration and baseline prednisone dose will be included in the base model for the analysis of the co-primary efficacy endpoints. Due to smaller sample size in the analysis, we will remove one or both strata from the analysis model if the model does not converge.

In addition to the co-primary endpoints, baseline prednisone/prednisolone dose and disease duration will be used to stratify all secondary efficacy analyses.

8.3. Multiple Comparisons and Multiplicity

Because the study is terminated early, all endpoints will be tested at two-sided 5% level of significance and no adjustments will be made for multiplicity. Nominal p-values will be presented for each analysis.

9. DATA HANDLING CONVENTIONS

9.1. Premature Withdrawal and Missing Data

9.1.1. Premature Withdrawal

The reasons for subject withdrawal from the study will be recorded. Subjects who are withdrawn will not be replaced.

9.1.2. Missing Data

9.1.2.1. Co-primary Efficacy Endpoints

The co-primary efficacy endpoint of time to SR on minimal steroid therapy will be analyzed using the ITT. Subjects who discontinue from the study before the end of the study (Wk 60), or reach their last planned treatment visit without achieving SR on minimal steroid therapy, will be censored in the analysis at their last visit. Subjects who discontinue prematurely (prior to Week 60) will be censored at the time they discontinued. Subjects who reach Week 60 without remission will be censored at their last visit.

9.1.2.2. Remission

For the secondary endpoint of the proportion of subjects in remission on minimal steroid therapy at Week 60, subjects who discontinued treatment prior to Week 60 will be considered as not in remission at Week 60.

9.1.2.3. Concomitant Medications

Partial dates will be imputed for medication start dates in order to determine if a medication is prior or concomitant. Imputed dates will be kept in the final derived datasets. The start and stop dates as reported in the electronic case report form (eCRF) will be presented in the data listings.

Partial or missing medication start dates will be handled as follows:

- If a day is missing, then the day will be set to the first day of the month.
- If a day and month is missing and the year is non-missing, then the date will be set to January 1st.
- If the stop date for a medication is on or after the date of the first dose of study medication and no start date is reported, it will be assumed that the medication was ongoing from prior to the start of IP.

Partial or missing medication stop dates for medications that are not ongoing will be handled as follows:

- If a day is missing, then the day will be set to the last day of the month.
- If a day and month are missing and the year is non-missing, then the date will be set to December 31st.
- If the start date for a medication is during the pre-therapy or on-therapy periods (defined in Section [9.3.2](#)) and no stop date is reported, it will be assumed that the medication use was ongoing throughout the on-therapy and follow-up/individualized follow-up periods.

9.1.2.4. Adverse Events

Partial dates will be imputed for adverse event start dates. Imputed dates will be kept in the final derived datasets. The start and stop dates as reported in the electronic case report form (eCRF) will be presented in the data listings.

Partial or missing AE start dates will be handled as follows:

- If the AE start date year value is missing, the date uncertainty is too high to impute a rational date. Therefore, if the AE year value is missing, the imputed AE start date is set to NULL.
- If the AE start date year value is less than the treatment start date year value, the AE started before treatment. Therefore:
 - If AE month is missing, the imputed AE start date is set to the mid-year point (01JulYYYY).

- Else if AE month is not missing, the imputed AE start date is set to the mid-month point (15MONYYYY).
- If the AE start date year value is greater than the treatment start date year value, the AE started after treatment. Therefore:
 - If the AE month is missing, the imputed AE start date is set to the year start point (01JanYYYY).
 - Else if the AE month is not missing, the imputed AE start date is set to the later of (month start point (01MONYYYY), AE start reference date + 1 day).
- If the AE start date year value is equal to the treatment start date year value:
 - And if the AE month is missing the imputed AE start date is set to the AE reference start date + 1 day.
 - Else if the AE month is less than the treatment start month, the imputed AE start date is set to the mid-month point (15MONYYYY).
 - Else if the AE month is equal to the treatment start date month or greater than the treatment start date month, the imputed AE start date is set to the later of (month start point (01MONYYYY), AE start reference date + 1 day).

Any AE with a missing start date will be considered a treatment emergent event, as defined in Section 9.3.2.

- Partial or missing AE stop dates will be handled as follows:
- If a day is missing, then the day will be set to the last day of the month.
- If a day and month are missing, then the date will be set to December 31st.
- However, if the imputation results in a date that is after the date of the last dose of study treatment, then the date of the last dose will be used as the imputed AE stop date.

Start or end dates which are completely missing (i.e. no year specified) will remain missing, with no imputation applied.

Imputed dates will be kept in the final derived datasets. The start and stop dates as reported in the eCRF will be presented in the data listings.

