9.3.2. Therapy Periods

For classifying AEs, infections, injection site reactions, cardiac events, liver events, medications, and non-drug therapies, the therapy periods will be defined as:

- **Pre-therapy:** If the onset date of the event is before the start date of study medication, the event will be considered pre-therapy. If the onset date of the event is on the start date of study medication, the event will be considered as on-therapy.
- **On-therapy (Treatment-emergent):** If the onset date of the event is on or after the start date of study medication and on or before 4 weeks after the date of last dose, the event will be considered on-therapy.

- **Follow-up:** For all subjects who do not enter the Individualized Follow-up Period, if the onset date of the event is after 4 weeks after the date of last dose, the event will be considered a follow-up event.
- **Individualized Follow-up:** For all subjects identified as entering the Individualized Follow-up period, events with an onset date after 4 weeks after the date of last dose will be considered individualized follow-up events.

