12.2. Adverse Events

AEs will be collected from the start of study treatment (treatment emergent AEs) through the follow-up contact.

SAEs will be collected over the same time period as stated above for AEs. However, any SAEs assessed as related to study participation (e.g., study treatment, protocol-mandated procedures, invasive tests, or change in existing therapy) or related to a concomitant medication, will be recorded from the time a subject consents to participate in the study up to and including any follow up contact.

AEs will be categorized by their occurrence in regard to therapeutic period (pre-therapy, on-therapy, follow-up or individualized follow-up) as defined in Section 9.3.2. Any events that occur prior to initiation of investigational product will be reported as medical history. If, however, a prior event is reported on the AE page of the eCRF it will be reported as 'pre-therapy' AE. Pre-therapy AEs will be presented only in data listings and will not be summarized.

All AEs will be coded using Medical Dictionary for Regulatory Activities (MedDRA) and summarized based on system organ class (SOC) and PT. Summaries by treatment group of the number and percentage of subjects with an AE will be presented in alphabetical order by SOC. Within the SOC level, the PTs will be presented in descending order of incidences. A PT will not be presented if no AEs occur within the level.

An overview summary of the number and percentage of subjects with any AE and the total number of AEs recorded during the randomized treatment period will be presented by treatment group. For the AEs recorded in the follow-up (FU) period if there are not enough events to summarize (i.e. <10 events) then the data of those AEs will be listed only otherwise it will be summarized. If any AEs recorded in the individualized follow-up period it will be listed only.

For AE listings, AE duration will be defined as (the date of resolution of the AE – the onset date of the AE) + 1 day. If no date of resolution is provided, AE duration will be presented as 'Continuing'.

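### Two branches of the partial AE start-date rule ignore the stop date, so an event that ended before first dose can be counted as treatment-emergent

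*SAP*

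**What the plan says.** SAP 9.1.2.4 sorts partial AE start dates by comparing year and month with the treatment start date.

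- **Earlier year:** "If the AE start date year value is less than the treatment start date year value, the AE started before treatment". The start goes to 1 July, or to the 15th of the known month.
- **Same year, earlier month:** "Else if the AE month is less than the treatment start month, the imputed AE start date is set to the mid-month point (15MONYYYY").
- **Same year, month missing:** "And if the AE month is missing the imputed AE start date is set to the AE reference start date + 1 day".
- **Same year, first-dose month or later, day missing:** "Else if the AE month is equal to the treatment start date month or greater than the treatment start date month", then "the imputed AE start date is set to the later of (month start point (01MONYYYY), AE start reference date + 1 day").
- **Start date entirely missing:** the event is treatment-emergent.

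No branch refers to the stop date. The conditions use the treatment start date, while the imputed value uses an AE reference start date (also written AE start reference date). Neither document defines that term.

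SAP 9.3.2 assigns the therapy period from onset alone: "If the onset date of the event is before the start date of study medication, the event will be considered pre-therapy", and onset on or after first dose, up to 4 weeks after the last dose, is on-therapy. SAP 12.2 foresees events from before dosing: "If, however, a prior event is reported on the AE page of the eCRF", it is to be reported as pre-therapy. Pre-therapy AEs are listed and not summarized.

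**The concern.** Treating an AE as treatment-emergent when its timing is unknown is a sound conservative default. It has no justification when a reported stop date shows that the event was over before first dose. In that case the imputation places onset after the event's own end, and SAP 9.3.2 then follows the imputed date.

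At stake are the on-therapy AE and SAE tables in SAP 12.2.2 and 12.3, which could include events that cannot be due to study drug. SAP 9.1.2.4 also keeps imputed dates in the final derived datasets, so the inconsistent record would persist there. The SAP already uses stop-date logic elsewhere: the medication rule in 9.1.2.3 compares a stop date with first dose. The AE rule has no counterpart.

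**Working it through.** There is no plan figure to reproduce. The check applies the start-date branches of SAP 9.1.2.4, then the period rule of 9.3.2, then the duration formula of 12.2.

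**Inputs.** The rules are from the SAP. All calendar dates are assumed for illustration: first dose D = 20-May-2015. The main reading is reference date = D.

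**General result.** In the two affected branches the imputed start is D + 1. For an event that stopped k days before first dose, duration = stop − onset + 1 = (D − k) − (D + 1) + 1 = −k. Onset D + 1 falls after D, so the event is on-therapy.

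| Reported start | Stop | Imputed start | Duration if imputed onset is used | Period |
|---|---|---|---|---|
| May-2015 | 10-May-2015 (k = 10) | 21-May-2015 | 10 − 21 + 1 = −10 | on-therapy |
| 2015, no month | 10-Mar-2015 (k = 21 + 30 + 20 = 71) | 21-May-2015 | −71 | on-therapy |
| May-2015 | 20-May-2015 (k = 0) | 21-May-2015 | 20 − 21 + 1 = 0 | on-therapy |
| Apr-2015 | 25-Apr-2015 | 15-Apr-2015 | 25 − 15 + 1 = 11 | pre-therapy |
| Apr-2015 | 10-Apr-2015 | 15-Apr-2015 | 10 − 15 + 1 = −4 | pre-therapy |
| Nov-2014 | 28-Nov-2014 | 15-Nov-2014 | 28 − 15 + 1 = 14 | pre-therapy |

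The first two rows are misclassified. The third is not: an event ending on the day of first dose has not been shown to precede exposure, although its imputed start is still one day after its end. The last three rows show that the earlier-month and earlier-year branches keep the event pre-therapy, even where the duration is negative.

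**Partial stop date.** Start 2015 with no month, stop Apr-2015: the stop-date rule gives 30-Apr-2015, so the event ended before 20-May-2015 whatever the day. It is still imputed to start on 21-May-2015 and classed on-therapy.

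**Sensitivity to the undefined term.** Suppose the reference date were consent, 84 days before dosing (the 12-week screening maximum): 20-May-2015 − 84 = 25-Feb-2015. Month missing with stop 10-Mar-2015 then gives start 26-Feb-2015 and duration 13 days (2 + 10 + 1), pre-therapy. Start May-2015 with stop 10-May-2015 gives the later of 1-May and 26-Feb, so 1-May-2015 and 10 days, pre-therapy. The misclassification therefore depends on reading the reference date as first dose.

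**Weight of one record.** SAP section 5 gives 69 randomized. Assuming an even split, an arm has 69/2 = 34.5 subjects, so one misclassified subject moves an incidence by at most 1/34.5 ≈ 2.9 percentage points.

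**The case against.** The other side has several fair points.

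- **Scope.** A reader might infer that partial AE start dates in general are pushed past first dose. They are not: among pre-dose events only the two same-year branches do this.
- **Undefined reference date.** With consent as the reference, both problem cases disappear. This stands as a stated assumption, but first dose is the better reading. Every branch condition compares with the treatment start date, and a reference at consent would make a month-missing AE pre-therapy while an AE with no start date at all is treatment-emergent.
- **Negative durations.** A reader might infer that the listings will show impossible durations. SAP 9.1.2.4 says listings present dates as reported on the eCRF, and SAP 12.2 does not say whether duration uses the imputed onset. The result is possible, not stated. The misclassification does not depend on it.
- **Exposure.** A reader might infer that any event earlier in the dosing year is at risk. AE collection starts with treatment (Protocol 6.3.7, SAP 12.2) and earlier events go to medical history. What remains is study-related SAEs from consent and prior events entered on the AE page anyway. SAEs are reported within 24 hours, so one with an unknown start month but a known stop date should be rare.
- **Consequence.** Safety analyses are descriptive, the rule is the same in both arms, and the by-subject listing with reported dates would let a reader spot the problem.

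These points limit the size of the problem. They do not reconcile 9.1.2.4 with 12.2: followed as written, under the natural reading, the rule summarizes events that the SAP says are to be listed only.

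**Conclusion.** The defect is real but narrow. It needs a start in the treatment-start year with the month missing, or in the first-dose month with the day missing, together with a stop date that shows the event ended before first dose. It rests on one assumption, that the reference date is first dose. Zero or negative durations need a second, that duration uses the imputed onset.

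The number of affected records is not in the documents; it is probably small and may be zero. The documents do not support a claim that the safety comparison is materially distorted. It is worth correcting because a written rule gives a wrong classification when followed, and in arms of about 34 or 35 subjects a single misplaced SAE would be visible. It does not affect efficacy.

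**What to change.** In SAP 9.1.2.4:

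1. Define the AE reference start date as the date of first dose and use one term throughout.
2. Add: if the reported stop date precedes first dose (a complete date, or a partial one whose year and month already show this), classify the event as pre-therapy and set the imputed start no later than the stop date.
3. Apply the same check to AEs with a missing start date before defaulting them to treatment-emergent.
4. Keep the treatment-emergent default where the stop date is missing, uninformative, or on or after first dose, and cap the imputed start at a complete stop date.

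In SAP 12.2, state whether AE duration uses the reported or the imputed onset.

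The cost is a few sentences and a small change to the derivation program. On-therapy counts may fall slightly. The conservative default is kept wherever the timing is truly unknown.
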